10.6.4.2. Extensive Triplicate ECGs

Extensive triplicate 12-lead ECGs, except for the food effect cohort, will be obtained to collect continuous 12-lead ECG data from pre-dose until 24 hours post-dose at the specified time points ([Table 1](#) and [Table 2](#)). Triplicate 10-second, 12-lead ECG recordings (digital ECGs) will be obtained within a 5-minute time window around the targeted time points outlined in the Schedule of Assessments described in [Table 1](#) for Part A (single dose administration) and [Table 2](#) for Part B (multiple dose administration). During the extensive triplicate 12-lead ECG assessment, meal intake should be avoided within 1 hour of ECG data collection.

Timing and recording technique for ECGs will be standardized for all subjects. Subjects will be required to lie quietly in a supine position with minimal movement and minimal exposure to noise and other environmental stimuli for at least 5 minutes before the ECG time point in order to allow for quality ECG data. All ECG data should occur in a 5-minute time window around the targeted time. If digital ECGs are artifactual and of poor quality, analyzable 10-

second ECGs will be repeated as close as possible to targeted time points. Actual time of the ECG recording will be used for the analysis.

The triplicate 10-second, 12-lead ECG time points post-dose are guided by PK animal data and are based around the estimated T_{max} . The time points may be changed depending on PK information obtained during the study from previous cohorts.

10.6.5. Columbia-Suicide Severity Rating Scale

The Columbia-Suicide Severity Rating Scale (C-SSRS) is a brief questionnaire that provides for the identification, quantification, and standardized assessment of the occurrences and severity of suicidal ideation and behavior. The C-SSRS will be assessed only after multiple dose administration (Part B). The “Baseline (Lifetime/Recent)” version of the C-SSRS will be assessed at screening ([Appendix C](#)). The C-SSRS “Since Last Visit” version will be assessed on other study days ([Appendix D](#)).

10.6.6. Peak Expiratory Flow Rate (PEFR) Measurement

Peak expiratory flow rate (PEFR) will be measured within a 30-minute time window around the targeted time points as outlined in the Schedule of Assessments in [Table 1](#) for Part A (single dose administration) and [Table 2](#) for Part B (multiple dose administration). The peak expiratory flow rate (PEFR, also known as a peak flow) is the maximum rate that a person can exhale during a short maximal expiratory effort after a full inspiration. Measurements will be performed in an upright position, with lips tightly closed around the mouth piece of the peak flow meter and blowing out as hard and as fast as possible into the meter.

10.6.7. Contraception and Pregnancy

The effects of SKL24741 on conception, pregnancy, and lactation in humans are not known. SKL24741 did not show any genotoxic potential in a standard battery of *in vitro* (Ames, human lymphocyte micronucleus) and *in vivo* (rat bone marrow micronucleus) studies (see [Investigator’s Brochure](#)).

10.6.7.1. Contraception

Subjects who can father a child must agree to use 2 highly effective methods of contraception, including at least one barrier method, as follows. Male subjects must use a condom with spermicide and if subject’s female partner is of childbearing potential, she must use 1 of the following highly effective methods of contraception:

- Hormonal contraception,
- Occlusive cap (cervical cap or diaphragm) with spermicide,
- Intrauterine device.

For male subjects with female partner(s) of non-childbearing potential (i.e., post-menopausal or post-surgical sterilization) at least 6 months before the first dose of study drug, no additional contraception method is required.

For all study subjects who can father a child with partners of child-bearing potential, all methods of contraception, including abstinence, must be used from the time of consent through 90 days after the last dose of study drug. Subjects whose partners become of child-bearing potential during the study must agree to the contraceptive requirements.

10.6.7.2. Pregnancy

If the female partner of a subject becomes pregnant, the subject must permanently discontinue study treatment. The investigator must notify the Medical Monitor, SK Life Science, Inc., and IQVIA by completing the Pregnancy Report form, faxing and emailing the form as per the Table of Contact ([Table 13](#) and [Table 14](#)), within 24 hours of the site's knowledge of the partner's pregnancy. The subject's treatment assignment will be unblinded, and if the subject was taking the active drug, the subject's partner will be followed until the end of pregnancy (e.g., delivery, miscarriage) and the infant exposed in-utero will be followed for 1 year after birth, provided consent is obtained. An ICF will be provided to explain these follow-up activities. Pregnancy does not constitute an adverse event.

11. STATISTICAL AND ANALYTICAL PLANS

This section presents a summary of the planned clinical pharmacology and safety analyses for this study. Safety statistical analysis details will be provided in the Statistical Analysis Plan (SAP) for this study, and clinical pharmacologic analysis details (including the definition of the PK population) will be provided in the Clinical Pharmacology Data Analysis Plan (CPAP), both of which will be finalized prior to clinical database lock.

Final analyses will take place after all subjects have completed the study and all data have been entered in the clinical study database.

11.1. Sample Size and Power

No formal sample size calculations have been performed. This study utilizes the sample size, or the number of subjects, that is commonly employed in early clinical pharmacology studies, in order to achieve the study objectives. Subjects who do not complete all the treatments and assessments specified in this protocol may be replaced.

11.2. Analysis Populations

- **Safety Population:** All subjects who were randomized and received at least 1 dose of study drug.
- **PK Population:** All subjects who received at least 1 dose of study drug and have sufficient PK data without any major protocol deviations.

All subject (randomized or dosed) data will be presented in the subject data listings.

11.3. Clinical Pharmacology Analysis

11.3.1. Pharmacokinetic Analysis

The PK analysis of SKL24741 (R-enantiomer) and SKL24742 (S-enantiomer) (if appropriate) will be performed using non-compartmental analysis (NCA) method.

The following PK parameters will be calculated for SKL24741 and SKL24742 (if appropriate) for the plasma concentration-time profile: Maximum concentration (C_{max}), time to maximum concentration (t_{max}), area under the concentration-time curve (AUC) from 0 to infinity (AUC_{∞}), AUC from time 0 to a given time t (AUC_t), AUC over the dosing interval (AUC_{τ}), apparent clearance (CL/F), apparent volume of distribution (V_d/F), half-life ($t_{1/2}$), and accumulation ratio (R_{acc}). In addition, the fraction excreted unchanged in the urine (f_e) and renal clearance (CL_R) will be calculated, if deemed appropriate. If SKL24741 metabolites are quantified in this study, appropriate PK parameters will be calculated for metabolites. Other PK parameters will be determined, as deemed appropriate.

A detailed description of the planned PK analysis will be presented in the CPAP. Statistical analyses on PK data may be performed if deemed appropriate.

11.4. Statistical Analysis

This section presents a summary of the planned statistical analyses of safety for this study. Statistical analysis details will be provided in the SAP for this study, which will be finalized prior to clinical database lock.

11.4.1. General Considerations

The SK Life Science, Inc. Biometrics designated CRO will analyze the safety data derived from this study. Only descriptive analyses will be performed; no statistical hypothesis testing will be done. Continuous variables (e.g., age) and PK parameters will be summarized by means of descriptive statistics (e.g., number of subjects (n), arithmetic mean, arithmetic standard deviation (SD), standard error of the mean (SEM), coefficient of variation (CV), geometric mean, geometric CV, median, first and third quartiles, minimum, and maximum). If the measurements in the source (raw) data are integers, then the corresponding mean and median will be presented to 1 decimal place and the SD to 2 decimal places; if the measurements are obtained to 1 decimal place, then the mean and median will be presented to 2 decimal places and the SD to 3 decimal places; and so forth. Minimum and maximum will be displayed as reported in the source (raw) data. Categorical variables (e.g., presence of an adverse event) will be summarized using counts and percentages. Percentages will be presented to 1 decimal place unless otherwise specified. Statistical analysis results will be presented by treatment group and as appropriate.

All subject data, including derived, will be presented in the subject data listings; listings will display all subjects who were randomized and/or dosed with the study drug.

11.4.2. Background Characteristics

11.4.2.1. Subject Disposition

The number and percentage of subjects in each disposition category (e.g., randomized, completing treatment period, completing the Follow-up visit, and discontinuing study with a breakdown of the reasons for discontinuation) will be summarized by the treatment group.

11.4.2.2. Demographics and Baseline Characteristics

Demographic, parameters and baseline characteristics will be summarized for the Safety Population. Continuous variables will be summarized by descriptive summary statistics and categorical variables by the number and percentage of participants.

11.4.2.3. Medical History

Medical history encompassing abnormalities and surgeries reported before the Screening visit will be coded using the Medical Dictionary for Regulatory Activities (MedDRA), version 19.0 or newer.

11.4.2.4. Prior and Concomitant Medications

Medications will be coded using the World Health Organization-Drug Dictionary (WHO-DD) and summarized by medication class and preferred term for the Safety Population as frequency tables in 2 parts:

- **Prior medication:** medication received between the Screening visit and the dose of study drug in Part A, and between the Screening visit and the first dose of study drug in Part B, regardless of when dosing of the medication ended,
- **Concomitant medication:** medication received at or after the dose of the study drug in Part A or the first dose of study drug in Part B.

If the medication start date is **on or after** the date of initial dosing of the study drug, then medication will be summarized as concomitant medication regardless of the medication end date. If the medication end date is **before** the date of initial dosing of the study drug, then medication will be summarized as prior medication regardless of the medication start date. The prior and concomitant medications will be summarized separately.

11.4.2.5. Study Drug Exposure

Exposure to study drug in Part B (multiple dose administration) will be defined as total number of days treated with study drug during the study, with total days calculated as last day of study drug minus first day of study drug plus 1 day.

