Part B is a multiple-dose escalation study in 32 healthy male subjects. Doses, dosing regimen, and food status (fasting vs. fed) used in Part B will be determined based on the outcome of Part A. Dosing will extend over a 14-day period at each dose level. Four dose levels will be assessed, and subjects will be randomized into one of the four dose levels. Each dosing cohort will have 8 new subjects (6 subjects randomized to SKL24741 and 2 to placebo) dosed each day for 14 days ([Table 4](#)). Daily dose level in Part B will not exceed the maximum dose level used in Part A.

At each dose level, a sentinel dosing strategy will be used as described in Section [7.2](#).

Table 4: Study Design

Part A: Single Ascending Doses (SAD)			
Total Number of Subjects	Randomized Stratification (Active/Placebo)	Number of Subjects per Cohort	Food Status (Fasting/Fed)
60 Male Subjects	10 mg SKL24741/Placebo	4 SKL24741/ 2 Placebo	Fasting

	25 mg SKL24741/Placebo	4 SKL24741/ 2 Placebo	Fasting
	50 mg SKL24741/Placebo	4 SKL24741/ 2 Placebo	Fasting
	100 mg SKL24741/Placebo	4 SKL24741/ 2 Placebo	Fasting
	200 mg SKL24741/Placebo	4 SKL24741/ 2 Placebo	Fasting
	300 mg SKL24741/Placebo	4 SKL24741/ 2 Placebo	Fasting
	400 mg SKL24741/Placebo	4 SKL24741/ 2 Placebo	Fasting
	600 mg SKL24741/Placebo	4 SKL24741/ 2 Placebo	Fasting
	800 mg SKL24741/Placebo	4 SKL24741/ 2 Placebo	Fasting
	1000 mg SKL24741/Placebo	4 SKL24741/ 2 Placebo	Fasting

Part A: Food Effect Assessment

Total Number of Subjects	Dose	Number of Subjects per Cohort	Food Status (Fasting/Fed)
6 Male Subjects*	Based on the outcome of Part A	6 SKL24741	Fed

Part A: Gender Effect Assessment

Total Number of Subjects	Dose	Number of Subjects per Cohort	Food Status (Fasting/Fed)
6 Female Subjects (non-childbearing potential)	Based on the outcome of Part A	6 SKL24741	Fasting

Note:

- All doses are in a capsule formulation.
- Subjects will remain in the clinic for a 4-night stay (discharged on Study Day 4).
- A sentinel dosing strategy (Section 7.2) will be used for all cohorts, except for food and gender effect cohorts, in Part A.

* Refer to Section 7.1 regarding the subjects returning to the CRU for the food effect assessment.

Part B: Multiple Ascending Doses (MAD)

Total Number of Subjects	Randomized Stratification (Active/Placebo)	Number of Subjects per Cohort	Food Status (Fasting/Fed)
32 Male Subjects	SKL24741 Dose 1/Placebo	6 SKL24741/2 Placebo	Based on the outcome of Part A

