- No fluids except those required for breakfast and dose administration will be allowed for two hours before and two hours after dose administration.

Part B – Multiple Dose Administration:

Subjects will be dosed each day for 14 days. Doses, dosing regimen, and food status (fasting vs. fed) will be based on the outcome of Part A.

In both Part A and Part B, study drug administration instructions are as follows:

- Study drug will be administered only after the indwelling catheter is placed (if applicable) and after pre-dose vital signs, peak expiratory flow rate (PEFR), and ECG are performed,
- In Part B, study drug will be given at approximately the same time (within a 1-hour window) on each dosing occasion,
- Study drug will be given as an oral capsule. Subjects will receive the study drug in an upright position. Subjects will be instructed not to lie down for 4 hours after taking the study drug, with the exception of study-specific events or assessments (sitting in an upright or reclining position [at least 45 degrees] is acceptable),
- The investigator (or his/her designee) will supervise dosing and conduct a mouth inspection of each subject to ensure that the study drug was taken.

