11.4.2.6. Study Drug Compliance

As the study drug will be administered under direct supervision at the study site, no analysis of compliance will be performed.

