11.4.4.1. Adverse Events

Adverse events will be coded according to Medical Dictionary for Regulatory Activities (MedDRA). The number and percentage of subjects experiencing an adverse event will be summarized by the MedDRA system organ class and preferred term, as well as by dose received. Adverse events will be classified as pre-treatment or treatment-emergent.

Pre-treatment adverse events are defined as adverse events that were reported or worsened after signing the ICF up to start of study medication.

Treatment-emergent adverse events are defined as adverse events that were reported or worsened on or after start of study medication through the Follow-up visit.

Only treatment-emergent adverse events will be summarized in tables. Treatment-emergent adverse events will hereafter be referred to as “adverse events.”

The incidence of adverse events will be summarized. Adverse event summaries will include the following:

- All adverse events (regardless of severity or relationship to study drug)
- SAEs
- Adverse events by severity
- Adverse events by relationship to study drug
- Adverse events leading to discontinuations
- Adverse events leading to deaths

Adverse event summaries will be presented by MedDRA System Organ Class and Preferred Term. A subject with multiple occurrences of the same adverse event or a continuing adverse event will be counted once, and only the maximum severity level will be presented in the severity summaries, and the worst relationship level in the relationship summaries.

Adverse events will be listed separately for those leading to death, SAEs, dose interruption, and permanent discontinuation.

All adverse events through the Follow-up visit will be listed in an individual subject data listing, including pre-treatment adverse events.

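### Part B exposure is defined as days treated but calculated as a calendar span, so it is overstated for any subject who misses a day and then resumes dosing

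*Protocol*

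**What the plan says.** Protocol Section 11.4.2.5 (Study Drug Exposure) states that exposure in Part B "will be defined as total number of days treated with study drug during the study". The same sentence then fixes the calculation: "total days calculated as last day of study drug minus first day of study drug plus 1 day". Nothing in it subtracts days without a dose.

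Three other places bear on this:

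- Section 9.3 (Administration), Part B: "Subjects will be dosed each day for 14 days". Section 7.1 gives the cohort size: "Each dosing cohort will have 8 new subjects (6 subjects randomized to SKL24741 and 2 to placebo) dosed each day for 14 days".
- Section 11.4.4.1 (Adverse Events): "Adverse events will be listed separately for those leading to death, SAEs, dose interruption, and permanent discontinuation". Interruption and permanent discontinuation are separate categories.
- Section 11.4.2.6 (Study Drug Compliance): because dosing is supervised, "no analysis of compliance will be performed".

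**The concern.** The definition and the formula describe two different quantities under one name. A subject dosed on Days 1 and 14 but not on some days in between has 14 days by the formula and fewer by the definition. Whoever programs the table must break one half of the sentence to follow the other. Since the arithmetic is the explicit part, it is likely to win.

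This is not a detail left for the SAP. The protocol defers several items to the SAP by name, such as the baseline definitions in Sections 11.4.4.2 to 11.4.4.4, but it writes this formula out itself. A SAP that follows it inherits the mismatch.

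At stake is one descriptive figure, the number of days on which Part B subjects received study drug. The Part B primary objective is safety and tolerability over 14 days of dosing, so readers will use that figure to judge how much dosing stands behind the safety data. With no compliance analysis planned, the protocol specifies no other summary that counts undosed days.

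**Working it through.** **Inputs.** Planned duration is 14 daily dosing days (Sections 7.1 and 9.3). Each Part B cohort has 6 active subjects (Section 7.1). The number of missed days, k, is not in the protocol; it is taken here as an assumption, over the range 1 to 5, with dosing resumed and the last dose on Day 14.

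**Formulas.** Span = last dosing day − first dosing day + 1. Count = number of distinct days with a dose. Span − count = number of undosed days between first and last dose, which cannot be negative, so the formula can never understate.

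**Plan's own figure.** Uninterrupted course: 14 − 1 + 1 = 14, and the count is 14. The two agree.

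**Permanent discontinuation without a gap.** Last dose on Day 3, 5, 7 or 10: span = 3, 5, 7, 10; count = 3, 5, 7, 10. The two agree.

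**Interruption, then resumption to Day 14.** Span stays at 14; count = 14 − k; relative overstatement = 14/(14 − k) − 1.

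| k (assumed) | Formula | Days dosed | Overstatement |
|---|---|---|---|
| 1 | 14 | 13 | 7.7% |
| 2 | 14 | 12 | 16.7% |
| 3 | 14 | 11 | 27.3% |
| 4 | 14 | 10 | 40.0% |
| 5 | 14 | 9 | 55.6% |

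**Mean over 6 active subjects.** With m subjects each missing k days, the true mean is (6 × 14 − m × k)/6, while the formula gives 84/6 = 14.0.

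- m = 1, k = 1: 83/6 = 13.83, so 14.0 is 1.2% too high.
- m = 1, k = 3: 81/6 = 13.50, 3.7% too high.
- m = 2, k = 3: 78/6 = 13.00, 7.7% too high.
- m = 3, k = 3: 75/6 = 12.50, 12.0% too high.
- m = 3, k = 5: 69/6 = 11.50, 21.7% too high.

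These are illustrations of scale. The protocol offers nothing from which to say how likely any row is.

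**The case against.** The best defence is that the case may never arise. Dosing takes place in the clinic under supervision with a mouth check (Section 9.9). The protocol gives no rule for withholding and resuming doses. Its stated responses to poor tolerability are removal of the subject (Section 8.4) and discontinuation of dosing at cohort thresholds (Section 7.3). For subjects who stop for good without a gap, the formula is exact. All of this stands, and it limits the size of the problem. It does not remove the mismatch: Section 11.4.4.1 still makes room for interruption apart from discontinuation, and supervision shows that a dose given was swallowed, not that every scheduled dose was given.

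Three stronger readings are tempting, and the protocol does not support them.

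- *Interruptions would be hidden.* They would be absent from the exposure summary only. Adverse events leading to interruption are listed separately (Section 11.4.4.1), and all subject data go into listings (Section 11.4.1). The pre-dose plasma samples on Days 3 to 6 and 9 to 13 (Section 10.3.1) give further information on drug levels.
- *Exposure is overstated where tolerability is worst, at the highest doses.* Subjects who stop for good because of intolerance are those for whom the formula is right. The protocol describes a steep dose response in animals, but the drug has not been studied in humans and Part B doses are not yet set, so clustering at high doses is an inference.
- *The safety conclusions are biased.* Adverse event summaries use numbers and percentages of subjects, and the analysis is descriptive without hypothesis tests. No planned analysis in the protocol uses days of exposure as a denominator, so no adverse event percentage changes.

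**Conclusion.** The point holds as an internal inconsistency in Section 11.4.2.5. The stated formula does not compute the stated quantity when a subject misses one or more days and then resumes. The error goes only upward: k days per affected subject, or 7.7% to 55.6% for k = 1 to 5 when the last dose falls on Day 14. Those percentages rest entirely on the assumed k and on resumption to Day 14. The effect is zero if nobody is interrupted, which is plausible in a supervised unit, and zero for discontinuation without a gap.

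The consequence is a descriptive exposure table that may be wrong for a few subjects; in cohorts of 6 active subjects, even one or two can shift a mean. No safety result is put in doubt. Severity is low: good to correct, not a reason to hold the protocol.

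**What to change.** In Section 11.4.2.5, calculate days treated as the number of days with at least one recorded administration of study drug. If last day minus first day plus 1 is also wanted, keep it under a separate label, such as duration of treatment, so that the two figures can be read side by side and any difference shows the undosed days.

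The cost is one sentence in the protocol, carried into the SAP and the table shell. Every dose is given under direct supervision and dispensing is recorded (Sections 9.7 and 9.9), so no new procedure should be needed. A per-subject count of missed doses or of total milligrams received would be an optional addition and is not needed to remove the error. The change affects no dose, schedule or rule for stopping treatment.
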